8.7.3 Vital signs

Vital sign assessments are performed in order to characterize basic body function. The parameters collected are the following: systolic and diastolic blood pressure (mmHg), body temperature ($^{\circ}$ C), heart rate (beats/min) and respiratory rate (breaths/min). The observed values and change from baseline will be summarized by descriptive statistics at each windowed visit. By-subject listings will also be provided.

8.7.4 Brief Neurological Assessment

All neurological assessment data and abnormalities will be listed (including pre-treatment and post-treatment results). The count and percentage will be provided by treatment group and visit.

8.7.5 Physical examinations

All physical examination data and abnormalities will be listed (including pre-treatment and post-treatment results). The count and percentage of normal vs. abnormal assessments will be provided by treatment group and visit.

8.7.6 Electrocardiograms

Electrocardiogram data (e.g., heart rate, PR, QTcF intervals, etc.) will be presented in listings by subject and collection date/time. A complete ECG assessment will be analyzed and reported in a separate ECG report from ERT.

8.7.7 SOWS

The Subjective Opiate Withdrawal Scale (SOWS) is a self-administered scale for grading opioid withdrawal symptoms. It contains 16 symptoms whose intensity the subject rates on a scale of 0 ("not at all") to 4 ("extremely"). In this study, subjects will complete SOWS daily for 14 days, starting at the off-treatment visit through the washout and safety follow-up period visit to the last visit on the study. Any subjects who are discontinued from investigational product will complete the SOWS daily for the 14 days following the last dose of investigational product (unless consent is withdrawn).

SOWS total scores and the individual item scores will be summarized descriptively by day (there are 14 days of SOWS) and treatment.

Categories of SOWS total score (mild: ≤ 10 ; moderate: 11 – 20; and severe: 21 – 30; and > 30) will be provided by count and percentage by day and treatment.

By-subject listings will also be provided.

8.7.8 Pharmacokinetic analysis

Investigational product plasma concentration data (nalbuphine and metabolites) will be listed by collection time, as applicable. Details will be summarized in a bioanalytical report generated by Covance Labs and appended to the CSR. Additional PK/PD analyses may be performed and presented in a separate document and may be appended to the CSR.

8.8 Primary analysis

The primary study analyses will be performed when the last subject has completed the double-blind treatment period. This will be documented in a full clinical study report. Final analyses and an addendum clinical study report will be performed when the last subject has completed the Week 56 phone call.

8.8.1 Interim analysis (Adaptive Sample Size Re-estimation)

The sample size re-estimation will be performed by one unblinded study statistician, who will not have a decision-making role in the trial; no one else, including Sponsor or clinical team members, will see the data presented in the Data Monitoring Committee (DMC). The communication plan from the DMC is to report one of the following statements based on the conditional power results: 1) “carry on”; 2) “increase sample size to XXX”; or 3) “stop the study due to unfavorable safety and/or efficacy concern.” Details about the DMC and the data monitoring procedures are specified in the DMC charter. When 50% of the subjects have provided the Week 14 primary endpoint data or have terminated the study and the data are considered “lockable” by data management, the data file will be provided with access limited to the specified unblinded statistician in the DMC; the proportion of responders will be estimated; and the conditional power (CP) will be calculated. Given that the interim analysis is to be performed at 50% of the initial sample size (120 subjects), the targeted power is 90%, and the maximum allowable sample size is set at 1.5 times the initial sample size (360 subjects), the conditional power cut-off value (CPmin) is 41%⁸. If the CP is between 41% and 90%, the number of subjects per treatment arm will be increased, up

to the maximum allowable sample size for this study ($120 \times 1.5 = 180$ each group), to recover the targeted power of 90%.

Since sample size re-estimation occurs only when the interim conditional power falls in the pre-specified “promising” range. The study will not stop for efficacy regardless of the conditional power; the overall alpha will be protected; and the final analysis will be carried out using conventional tests, without the need for weighing the stage 1 and 2 results or adjusting the alpha value.

9 CHANGES TO PLANNED ANALYSIS FROM STUDY PROTOCOL

The following changes were agreed upon

1. Sites were changed from random effects to region (US or Europe) which is being treated as a fixed effect.
2. LOCF was excluded from imputation methods.
3. The ranked outcome for adjustment for multiplicity was changed. The ItchyQoL measure & the PROMIS scale were excluded from the ranking and replaced with PAS (5a)
4. The analyses for prohibited medication were changed to set all efficacy outcomes to missing from the date of ingestion of the prohibited medication. Previously, missing outcomes were set = non-responders.
5. A new set of simple multiple imputation models were added to assess the impact of missing efficacy measures due to the use of prohibited medications.

11 VERSION HISTORY

Version	Date	Notes
Draft 1.0	27Aug2018	First draft base on Protocol V1.0
Draft 2.0	10Oct2018	Stable version after addressing Trevi review comments and incorporating changes in Protocol Amendment 1 (Protocol V2.0)
Final 1.0	15Mar2019	Final version after incorporating changes in Protocol Amendment 2 (Protocol V3.1)
Draft V1.4	19Feb 2022	Version above modified after several meetings with TREVI in 2021 & 2022 as clarified in comments above.
Draft V1.5	9Mar2022	Version above modified after several meetings with TREVI in 2021 & 2022 as clarified in comments above. V1.5 had modified section of TPA. The analysis has been refined here & an updated Guidance document added to the Appendix.
Draft V1.6	23Mar 2022	Version above modified after several meetings with TREVI in 2021 & 2022 as clarified in comments above. V1.5 had modified section of TPA. The analysis has been refined here & an updated Guidance document added to the Appendix. Proc GENMOD has been modified as well.
Final 2.0	25 th March 2022	Modified rank order of the outcomes to address issues of multiplicity & efficacy outcomes for subjects who took Prohibited Medications
Final 2.1	01 June 2022	Changed Compliance cut off to 50%. Changed Efficacy Analysis from Proc Glimmix to Proc Genmod because of convergence issues. Reduced number of imputations from 1000 to 50 to increase efficiency.

12 APPENDIX

12.3 Programming Guidance Document for Multiple Imputation, Control –based Imputation & Tipping Point Analysis

Introduction.

This appendix describes three approaches to multiple imputation.

1. Simple Multiple Imputation;
2. Control- based Imputation;
3. Tipping Point Analysis.

All of these are being implemented in data sets that have repeated measures data collected from subjects at multiple time points.

The primary efficacy endpoint is defined as the difference between the percentage of “Responders” at Week 14 for the NAL ER treatment arm versus the placebo arm. A “Responder” is defined as a subject with a ≥ 4 -point decrease in the 7-day average WI-NRS from baseline to Week 14.”

Secondary endpoints are:

- The mean change in ItchyQoL from baseline to Week 14 for the NAL ER treatment arm versus the placebo arm;
- Change in PAS as assessed by the percentage of subjects having a 1-category improvement in the percentage of prurigenous lesions with excoriations/crusts (item 5a) from baseline to Week 14 for the NAL ER treatment arm versus the placebo arm;
- The mean change in sleep disturbance (PROMIS Sleep Disturbance Short Form 8a) from baseline to Week 14 for the NAL ER treatment arm versus the placebo arm.

Multiple imputation is a missing data approach that assumes that the missing data is missing at random (MAR), i.e., that the probability of missing is not a function of the values that are missing but only depend on the observed responses.

The advantage of MI over single imputation is that it allows one to adjust the variance to account for the imputation of the missing data.

All of the data sets on which imputation is applied are longitudinal data sets, specifically the following ADaM datasets: ADEFF and ADQS. Please note: ADEFF will use 4 visits (AVISITN 2-5/ Week 2, 6, 10, 14)

ADQS will use 3 visits (AVISITN 3-5/Week 6, 10, 14).

The following is an explanation of the process.

This is a guidance document. It does not provide the exact code to be implemented but describes the processes & principles that need to be followed in order to implement these analyses.

There are five steps in simple MI process.

1. Check missing data patterns;
2. Impute non-monotonic / intermittent data – leaving only monotone missing data;
3. Use monotone regression to impute monotone missing data & create multiply imputed data sets;
4. Run the efficacy analyses (PROC GENMOD, PROC MIXED) on the multiply imputed data sets;
5. Use PROC MIANALYZE to combine the efficacy output to get a single estimate from all the imputed data sets.

Step 1. Checking missing data patterns

For this study, the missing data patterns will be checked by treatment and visits 3 to 5.

There are 3 steps to this process:

Create dataset for efficacy measure including visits from baseline to week 14

```
data mi_chk1; set datax;
where param="" and paramcd="" and dtype="" and 3 <= visit <=5;
run;
```

Transpose dataset to display each visit as one column:

```
proc sort data = mi_chk1; by treatment_id;
proc transpose data=mi_chk1 out=mi_chk2 prefix="";
by treatment_id;
id avisitn;
var aval;
run;
```

Use PROC MI with the NIMPUTE=0 option to create the "Missing Data Patterns" table for the specified variables:

```
ods output MissPattern=missp;
proc mi data=mi_chk2 NIMPUTE=0;
  by treatment;
  var visit3 – visit5;
run;
/*Add baseline to estimate change from baseline*/
```

```
proc sort data = mi_chk1; by id; data base; set mi_chk1 (Keep = id base country); by id; if first.id;
run;
proc sort data = mi_chk2; by id;
proc sort data = base; by id;
data mi_chk2; merge mi_chk2 base; by id;
run;
```

Step 2: Impute non-monotonic / intermittent data – leaving only monotone missing data.

Fill in the intermittent missing data using the following code.

```
proc sort data = mi_chk2; by treatment;
proc mi data=mi_chk2 seed=12345 NIMPUTE=50 out=MI;
by trt01pn;
mcmc impute=monotone;
var Visit3 – Visit5;
run;
```

Step 3. Use monotone regression to impute monotone missing data & create multiply imputed data sets.

Here the non-missing values for subjects in the control group are used to impute values for the subjects with missing values in the control group and similarly for the subjects in the active treatment group.

**Visit 3 values are imputed using baseline value and treatment;
visit 4 values are imputed using baseline, treatment and visit 3 & so on.**

```
proc sort data = mi; by _Imputation_;
proc mi data=mi out=mi_reg seed=54321 nimpute=1;
by _Imputation_;
var trt01pn base v3 v4 v5;
class trt01pn;
monotone regression;
run;
```

Convert the data set from a horizontal dataset, i.e. one row per subject to a vertical data set, i.e., multiple rows per subject.

```
Data mi_reg1; set mi_reg;
Visit = 1; WINRSA=base; output;
Visit = 2; WINRSA=v3; output;
visit = 3; WINRSA=v4; output;
visit = 4; WINRSA=v5; output;
drop v3 v4 v5;
run;
```

Step 4. Run the efficacy analyses (PROC GENMOD, PROC MIXED) on the multiply imputed data sets.

Create variables needed for the 50 data sets, e.g. RESP, Pooled Site, treatment coded as (0-Placebo,1-Treatment) etc.

1. Fit the models on the 50 imputed data sets by _Imputation_.

```
proc sort data = mi_reg1;
by _imputation_ visit trt;
```

```

ods select none; /*suppress printing the output*/

proc genmod data=winrsa descending; where avisitn ge 3;
class usubjid avisitn trt posite ;
model resp = trt avisitn avisitn*trt posite base
/dist=binomial;
repeated subject=usubjid / withinsubject=avisitn
type=un;
lsmeans trt*avisitn /cl ilink diff oddsratio;
Ods output diff=diff lsmeans=lsm ;
run;

```

Step 5. Combine estimates of the 50 GENMOD models to create an overall estimate and a relative efficacy score.

Due to the finicky nature of PROC MIANALYZE, the suggestion is to produce output to one effect at a time. This can be programmed in a macro.

Run three separate instances of GENMOD to get the effect for the interaction first, then the treatment & then visits

MIANALYZE cannot handle too many effects and too many variables in the input data sets, so subset to the needed effects. For the interaction, choose the estimate for the same visit but different treatments. That is what the next two statements do.

```

data diff_mi_nw; set diff_mi; where visit = _visit and trt ne _trt;run;
data diff_mi_nw2; set diff_mi_nw (keep = _imputation_ estimate stderr effect); run;

```

The data set diff_mi_nw2 is then fed into the Proc MIANALYZE:

```

proc mianalyze parms=diff_mi_nw2; /*where _imputation_ le 4;
modeleffects treatment*visit ;
run;

```

Since this is GENMOD the results should be presented as odds ratios (ORs). The final estimate & the SEs should be exponentiated to create the ORs.

Also fit the continuous ITCH score using Proc Mixed.

```

ods select none;
proc mixed data = mi_reg1; by _Imputation_ ;
class variables;
Model (Continuous endpoint) = Treatment, Baseline Vars, Time, Treatment * Time/solution
covb;
repeated ID/ type = cs subject = ID(treatment)
lsmeans Interaction Term/diff cl;

```

```
ods output Diffs=diff_mi LSMEANS=lsm_mi;
run;
ods select all;
```

Subset the data set to be input into MIANALYZE.
data diff_mi_nw; set diff_mi (keep = _imputation_
estimate stderr effect probt);
run;

```
proc mianalyze parms=diff_mi_nw;
modeleffects effect of interest (e.g., treatment, Visit or interaction but to be done one at a time);
run;
```

Control-Based Imputation.
STEPS 1-4 ARE EXACTLY AS DESCRIBED ABOVE.

The imputation of missing values is done one visit at a time.

The difference between this process and the simple multiple imputation above is primarily in the data management step where a dataset is created with all control subjects and only those trt = NALER subjects who have missing values for visit, one visit at a time.

Below is the suggested approach.

In this case use v3, v4 & v5. After the intermittent missing data is filled in, one would expect all v3 to be filled in & only v4 & v5 to be missing.

This is also a way to check & make sure that the data is behaving as expected.

- Step 1. Create two separate data sets, i.e., one with just control subjects and one with just NALER subjects;
- Step 2. Create a subset NALER data to include only those who have missing values for visit 4;
- Step 3. Set the Control data set and the dataset with V4 missing by _Imputation & usubjid.

Now, the dataset has all of the control subjects and only the NALER subjects with v4 missing in this data set.

Sample Program:

```

data control_mi; set mi; where trt = 0; run;
data trt_mi; set mi; where trt = 1;
data v4_trt_mi; set trt_mi; where v4 = .; run;
proc sort data = control_mi; by _imputation_usubjid;
proc sort data = v4_trt_mi; by _imputation_usubjid;
data mi_v4; set v4_trt_mi control_mi; by _imputation_usubjid;
run;

```

Then use monotone regression to impute the v4 values.

```

proc sort data = mi_v4; by _Imputation_;
proc mi data=mi_v4 out=mi_reg_v4 seed=54321 n impute=1;
by _Imputation_;
var base v3 v4
monotone regression (v4);
run;

```

Repeat for v5.

Then merge the data set back to include the full treatment = NALER data set with the non-missing & imputed values together. Set the Trt = 1 & trt = 0 data sets by _Imputation_ & usubjid

2. **Convert the data set from a horizontal dataset, i.e. one row per subject to a vertical data set, i.e., multiple rows per subject.**

```

Data mi_reg1; set mi_reg;
Visit = 1; WINRSA=base; output;

```

```
Visit = 2; WINRSA=v3; output;
visit = 3; WINRSA=v4; output;
visit = 4; WINRSA=v5; output;
drop v3 v4 v5;
run;
```

Create required variables needed in these 50 data sets, e.g. RESP, Pooled Site, treatment coded as (0,1) etc.

Run Proc GENMOD or Proc Mixed
Run Proc MIANALYZE

Tipping Point Analysis.

In this analyses, the concept is to assess the level of bias introduced by the missing at random assumption in the first simple MI performed above. In this approach, subtract a pre-determined value from the imputed values for the actively treated group. this approach uses the standard deviation of the scores for the completers in the treated group. It could be a %change in the mean or a variety of other values depending on the expected effect. The suggested approach is below.

```

data mi_chk1; set adeff;
where param="WINRS Average" and paramcd="WINRSA" and dtype="" and 2 <=avisitn<=5;
run;
data mi_chk1; set mi_chk1;
if trt01pn = 1 then trt = 1;
else if trt01pn = 2 then trt = 0;
run;

proc sort data = mi_chk1; by trt usubjid;
proc transpose data=mi_chk1 out=mi_chk2 prefix=v;
by trt usubjid;
id avisitn;
var aval;
run;
  by trt ;
  var v2-v5;
run;

```

Next estimate the standard deviation of the WINRS score in the control group and active treatment group by visit among those subjects who completed all visits.

Then merge a data set with the delta value to the data set where values will be imputed.

Use proc univariate to obtain the mean values, stddev, range for the completers in the treated group in order to identify a delta value (SD in this case. Other approaches could use the median, or percentiles).

Suggested code is below.

```

proc sort data = mi_chk1; by usubjid;
data base; set mi_chk1 ( Keep = usubjid base country complfl); by usubjid; if first.usubjid;run;
proc sort data = mi_chk2; by usubjid;
proc sort data = base; by usubjid;
data mi_chk2; merge mi_chk2 base; by usubjid;
run;
proc univariate data = mi_chk2; where complfl = 'Y'; by trt;
var v2 v3 v5 v5;
output out=WINRSCOMP_uni mean=Meanv2 Meanv3 meanv4 meanv5
      std=stdv2 stdv3 stdv4 stdv5
      range=range_v2 range_v3 range_v4 range_v5;
run;

```

```

proc sort data = WINRSCOMP_UNI; by trt;
data mi_chk3; merge mi_chk2 winrscomp_uni; by trt;
run;
  
```

Fill in the intermittent missing data using the following code.

```

proc sort data = mi_chk3; by treatment;
proc mi data=mi_chk3 seed=12345 NIMPUTE=50 out=MI;
  by trt01pn;
  mcmc impute=monotone;
  var Visit2 – Visit5;
run;
  
```

Create an id variable to identify which visits were imputed in the active treatment group.

```

data control_mi; set mi; where trt = 0; run;
data NALER_mi; set mi; where trt = 1;
Data NALER_MI; Set NALER_MI;
if V2 = . then Imp_v2 = 1; else Imp_V2 = 0;
if V3 = . then Imp_v3 = 1; else Imp_v3 = 0;
if v4 = . then Imp_v4 = 1; else Imp_v4 = 0;
if v5 = . then Imp_v5 = 1; else Imp_v5 = 0;
run;

proc sort data = control_mi; by trt_imputation_usubjid;
proc sort data = NALER_mi; by trt_imputation_usubjid;
data mi; set NALER_mi control_mi; by trt_imputation_usubjid;
run;
  
```

Imputing values in the monotone missing data using regression.

Visit 3 values are imputed using baseline value and treatment;

Visit 4 values are imputed using baseline, treatment and visit 3 & so on.

```

proc sort data = mi; by _Imputation_;
proc mi data=mi out=mi_reg seed=54321 n impute=1;
by _Imputation_;
var trt01pn base v3 v4 v5;
class trt01pn;
monotone regression;
run;
  
```

1. Tipping Point Analysis – Starts here:

Take each group of dropouts – those who dropped out at v3 & subtracting (or adding) the SD of the completers group for that visit from the imputed value.

Then merge it to the original data set.

Then go to the next set of dropouts.

```

data mi_reg2_Impv3; set mi_reg2;
if Imp_v3 = 1
then do;

  /*Create a macro where this value is replaced by the following: (-.25SD, -0.5SD, -
  0.75stddev, -SD, 0.25SD, 0.5SD, 0.75SD, SD), thus reducing the imputed values by a
  quarter, a half, three-quarter and a whole SD. Then, on the other side add 0.25SD, 0.5SD,
  0.75SD*/

v3 = v3-stdv3;
v4 = v4-stdv4;
v5 = v5-stdv5; (each of these is done only for visits that were imputed in the previous step)
end;
run;
proc sort data = mi_reg2; by _Imputation_usbjid;
proc sort data = mi_reg2_impv3; by _Imputation_usbjid;
data mi_reg4; merge mi_reg2 mi_reg2_impv3; by _Imputation_usbjid;
run;

data mi_reg4_Impv4; set mi_reg4;
if Imp_v4 = 1
then do;
v4 = v4-stdv4;
v5 = v5-stdv5;
end;
run;
proc sort data = mi_reg4; by _Imputation_usbjid;
proc sort data = mi_reg4_impv4; by _Imputation_usbjid;
data mi_reg5; merge mi_reg4 mi_reg4_impv4; by _Imputation_usbjid;
run;

data mi_reg5_Impv5; set mi_reg5;
if Imp_v5 = 1
then do;
v5 = v5-stdv5;
end;
run;
proc sort data = mi_reg5; by _Imputation_usbjid;

```

```

proc sort data = mi_reg5_impv5; by _Imputation_usubjid;
data mi_reg6; merge mi_reg5 mi_reg5_impv5; by _Imputation_usubjid;
run;
  
```

The result of the above steps is a modified horizontal data set with the modified imputed values. Now, proceed as before by converting this to a vertical data set & fitting GENMOD or MIXED.

2. Convert the data set from a horizontal dataset, i.e. one row per subject to a vertical data set, i.e., multiple rows per subject.

```

Data mi_reg1; set mi_reg;

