7.3.4. Prurigo Activity Score (PAS)

The PAS consists of 5 quantitative and qualitative measurements related to the examination of the skin: Type; number; distribution; quantitative number of lesions in a representative body part; and activity. Prurigo lesion activity is recorded as a stage (0 to 4), based on the percentage of overall lesions with the relevant characteristic.

Three types of PAS responders are defined, one for each of the following items: Prurigenous lesions with excoriations/crusts (item 5a); Healed lesions (item 5b); Number of lesions (item 2). For each of these, a responder is defined as a subject who has at least 1-category improvement in the relevant item from baseline to Week 14. For all three, a patient who does not have Week 14 measurement is a non-responder.

7.3.5. Investigator Global Assessment – Prurigo Nodularis (IGA-PN).

The IGA-PN collects an Investigator Global Assessment of the status of the PN skin lesions. The IGA-PN uses a 5-category scale (scoring 0 to 4) for assessing the status of 2 aspects of the disease: The Activity (amount of excoriation and crusting associated with the prurigo lesions), and the Stage (the quantitative presence and proportion of flattening of the lesions). An IGA-PN responder for Activity or Stage is defined as a subject who has at least 1-category improvement in the respective score from baseline to Week 14.

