- Change in PAS as assessed by the percentage of subjects having a 1-category improvement in the percentage of healed lesions (item 5b) from baseline to Week 14 for the NAL ER treatment arm versus the placebo arm;
- Change in PAS as assessed by the percentage of subjects having a 1-category improvement in the percentage number of lesions (item 2) from baseline to Week 14 for the NAL ER treatment arm versus the placebo arm;
- Change in IGA-PN as assessed by the percentage of subjects having a 1-category improvement in activity from baseline to Week 14 for the NAL ER treatment arm versus the placebo arm;
- Change in IGA-PN as assessed by the percentage of subjects having a 1-category improvement in stage from baseline to Week 14 for the NAL ER treatment arm versus the placebo arm;
- The proportion of subjects with PBI-P ≥ 1 at Week 14 for the NAL ER treatment arm versus the placebo arm;
- The proportion of subjects with PBI-P ≥ 2 at Week 14 for the NAL ER treatment arm versus the placebo arm;
- The proportion of subjects with PBI-P ≥ 3 at Week 14 for the NAL ER treatment arm versus the placebo arm.

In addition, shift tables from baseline for improved ≥ 1 , no change, worsened ≥ 1 , and discontinued at Week 14 will be presented for PAS (item 5a), PAS (item 5b), PAS (item 2), IGA-PN for Activity, and IGA-PN for Stage.

Logistic Regression for Categorical Endpoints

The logistic regression model used for the primary endpoint will also be used for several secondary efficacy endpoints. Subjects with missing Week 14 measurement are treated as non-responders. Response rate, standard error, OR between the treatment groups, 95% confidence interval and p-values will be provided. The endpoints are:

- Change in PAS as assessed by the percentage of subjects having a 1-category improvement in the percentage of pruriginous lesions with excoriations/crusts (item 5a) from baseline to Week 14 for the NAL ER treatment arm versus the placebo arm;
- Change in IGA-PN as assessed by the percentage of subjects having a 1-category improvement in activity from baseline to Week 14 for the NAL ER treatment arm versus the placebo arm (95% CI only, with no p-value).

Sensitivity analysis for PAS (item 5a)

The sensitivity analysis to assess the impact of concomitant medications use for the primary endpoint will also be used for PAS (item 5a).

For open-label period visits, descriptive statistics will be displayed by treatment and overall for all secondary variables.

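### PAS item 5a sensitivity analysis: the appendix imputes over a Week 6 visit at which PAS is not taken, using a linear model for a 0-4 category and no rule for deriving response

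*SAP*

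**What the plan says.** SAP 12.3 says imputation applies to longitudinal data sets, "specifically the following ADaM datasets: ADEFF and ADQS". It gives ADEFF Weeks 2, 6, 10 and 14; for the other, "ADQS will use 3 visits (AVISITN 3-5/Week 6, 10, 14". Its introduction restates the secondary endpoints, among them "Change in PAS as assessed by the percentage of subjects having a 1-category improvement in the percentage of prurigenous lesions with excoriations/crusts (item 5a". Step 2 fills intermittent gaps by MCMC on visits 3 to 5. Step 3 reads "Use monotone regression to impute monotone missing data & create multiply imputed data sets"; its model takes baseline, v3, v4 and v5, with each visit predicted from those before it.

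For the instrument, SAP 7.3.4 states: "Prurigo lesion activity is recorded as a stage (0 to 4), based on the percentage of overall lesions with the relevant characteristic". For response, "a responder is defined as a subject who has at least 1-category improvement in the relevant item from baseline to Week 14". For missing data, "For all three, a patient who does not have Week 14 measurement is a non-responder".

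SAP 8.6.3 adds one sensitivity analysis for this item: "The sensitivity analysis to assess the impact of concomitant medications use for the primary endpoint will also be used for PAS (item 5a". That analysis, SAP 8.6.1.3, sets efficacy data to missing once a listed medication is started and refers to the Appendix for missing-data handling. SAP 9, items 4 and 5, records that such data were previously scored as non-response and that simple multiple imputation models were added for them.

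**The concern.** The visit list and the model suit ItchyQoL and PROMIS, which are taken at Weeks 6, 10 and 14 and are treated as continuous. PAS item 5a fits neither. Applied to PAS, the procedure calls for a visit that does not exist and then treats an ordered category as a normal variable.

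PAS 5a is a key secondary endpoint, and this is the only sensitivity analysis that SAP 8.6.3 names for it. If the written procedure fails, whoever programs it must choose the visits, the model and the response rule, possibly after unblinding.

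**Working it through.** **1. Is there a Week 6 PAS value?** The sources agree that there is not.
- Protocol 9.1.3.3: the Week 6 list has ItchyQoL, the sleep scale and WI-NRS, but no PAS. The Week 10 and Week 14 lists include PAS.
- Protocol Table-1: PAS at screening, baseline, Week 10 and Week 14.
- SAP 7.2.7: the first post-baseline PAS window is Week 10, Days 29 to 84. Even an unscheduled Day 42 PAS would be labelled Week 10.

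**2. Can the step be fitted?** Observed v3 values for PAS = 0. The v3 model has 0 rows, and the v4 and v5 models, which use v3 as a predictor, have 0 complete rows. Holding PAS in ADEFF would not help, since Weeks 2 and 6 both lack PAS.

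**3. With Week 6 dropped, is linear imputation adequate?** Take a baseline of 3 and an imputed Week 14 value of 2.4. The raw change is 0.6, a non-response; the nearest category is 2, a response. The SAP does not say which applies.

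To size this I simulated one arm of 180 with 400 replicates and 5 imputations. Week 14 was imputed by Bayesian linear regression on baseline and Week 10. These assumptions are not in the documents: 25% missing at Week 14, 70% of those also missing at Week 10, missingness unrelated to outcome, latent Week 10-14 correlation 0.7, scores truncated to 0-4. Baseline shares in categories 1 to 4 were 2%, 8%, 20% and 70%. Negative change is improvement. Results are percent responders among imputed subjects.

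| Assumed change: probability | True | Raw | Rounded | Raw minus true |
|---|---|---|---|---|
| -2: .05, -1: .20, 0: .65, +1: .10 | 25.3 | 11.6 | 34.3 | -13.7 |
| -3: .05, -2: .10, -1: .20, 0: .55, +1: .10 | 35.1 | 28.4 | 49.5 | -6.7 |
| -3: .05, -2: .12, -1: .28, 0: .50, +1: .05 | 45.2 | 33.4 | 55.5 | -11.8 |
| -3: .10, -2: .17, -1: .28, 0: .40, +1: .05 | 54.8 | 45.4 | 64.4 | -9.4 |
| -4: .08, -3: .12, -2: .12, -1: .13, 0: .55 | 45.0 | 49.0 | 64.0 | +4.0 |
| -4: .05, -3: .08, -2: .07, -1: .05, 0: .75 | 25.0 | 35.5 | 52.7 | +10.5 |
| -4: .05, -3: .05, -2: .03, -1: .02, 0: .85 | 14.7 | 27.4 | 45.4 | +12.7 |

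A flatter baseline mix (10%, 20%, 30%, 40%) gave the same sign in every row, from -13.5 to +9.0. Over all 14 scenarios raw values were too low in 8 and too high in 6. Rounding was too high in all 14.

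**4. Effect on the whole arm.** Share missing x error among imputed: 0.25 x (-13.7) = -3.4 points; 0.25 x 12.7 = +3.2 points.

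**5. Effect of the unstated response rule.** Rounded minus raw runs from 64.0 - 49.0 = 15.0 points to 34.3 - 11.6 = 22.7 points among imputed subjects. Times 0.25, that is 3.8 to 5.7 points over the arm, from a choice the SAP leaves open.

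**The case against.** The strongest reply is that the SAP never says outright that PAS 5a is imputed this way. The appendix introduction only restates the secondary endpoints. SAP 7.4.1 names ItchyQoL and PROMIS for imputation, and SAP 8.6.3 ties its imputation text to continuous measures. PAS has its own non-responder rule, and nothing states that PAS sits in ADQS. This stands as a description: the route is indirect. It does not remove the problem. SAP 8.6.3 carries PAS 5a into the prohibited-medication analysis, SAP 8.6.1.3 sends that analysis to the Appendix, and SAP 9 says imputation models were added where non-response had been used before.

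A second reply is that the appendix calls itself guidance, and that the empty column would show at the Step 1 pattern check. That is probably right, and it means a wrong number is unlikely to slip through from the Week 6 error. But the appendix also says its processes and principles are to be followed. Seeing the failure tells the programmer nothing about the model or the response rule to use instead.

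A reader might infer that fractional values undercount responders and so work against NAL ER. The documents do not support this. The sign depends on the change distribution. The missingness here comes from prohibited-medication use, for which no rate by arm is given; TR03 non-completion is a different cause and cannot stand in for it.

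**Conclusion.** The point holds for one sensitivity analysis. Applied to PAS 5a, the stated visit set cannot be fitted; this follows from the documents alone. After Week 6 is dropped, linear imputation with no response rule can bias the imputed response rate in either direction. The sizes in the working rest on the assumed 25% missing and the assumed change distributions, and show scale only; they do not predict this trial.

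Two further inferences should be resisted. First, the confirmatory PAS 5a result is not in doubt on this ground: its logistic regression scores missing Week 14 data as non-response (SAP 7.3.4 and 8.6.3), and the primary endpoint is not touched. Second, SAP 9, item 3, might be read as moving PAS 5a up the testing order. It is third in Protocol 13.4.6.3 and fourth in the SAP 8.6 multiplicity list, so a rise is not shown.

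The sponsor should correct this before the analysis is programmed.

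**What to change.** - In SAP 12.3, state that imputation of PAS item 5a uses baseline, Week 10 and Week 14 only. In SAP 8.6.3, state explicitly that PAS 5a values removed after prohibited-medication use are imputed in this analysis.
- For PAS, replace both normal-theory steps. Use a categorical method for intermittent gaps, such as fully conditional specification with a cumulative logit in place of the Step 2 MCMC. Then use MONOTONE LOGISTIC on baseline category, Week 10 category, arm and region in place of the Step 3 linear regression. Changing Step 3 alone is not enough, because the MCMC could still leave a fractional Week 10 value as a predictor.
- For control-based imputation, fit the same model on control subjects only.
- Derive response from the imputed category under the SAP 7.3.4 definition, so that imputed and observed subjects are scored alike.
- Keep the three-visit linear model for ItchyQoL and PROMIS.

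The cost is a short appendix revision and some extra programming. Sparse categories may need collapsing, and the rule for that should be written down in advance.
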